5.2.1 Sample Size Justification

Approximately 24 subjects will be enrolled in this study. On Day 1, eligible subjects will be randomly assigned in a ratio of 1:1 (12 subjects per arm) to receive 1 of 2 study treatments (20 mg, OP0201 or placebo).

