5. SAMPLE SIZE

Approximately 24 Study Participants will be randomized. Additional Study Participants will be randomized for Study Participants who discontinue the study prematurely.

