8.3 General Analysis Conventions

Categorical variables will be summarized using frequencies and percentages. Percentages will be reported to one decimal place. Unless otherwise noted in Section 11, categorical variables will be analyzed using chi square tests of association or, if any contingency table cell has less than 5 subjects, Fisher's exact test.

Continuous variables will be summarized using descriptive statistics (e.g., n, mean, standard deviation, least-squares mean with standard error, distribution percentiles, range). The number of decimal places for minimums and maximums will be the same as the original data. The number of decimal places for means, medians, and interquartile ranges will be the same as the original data plus one. The number of decimal places for measures of variance will be the same as the original data plus two. Unless otherwise noted in Section 11, continuous variables will be analyzed using t-tests or a non-parametric alternative.

Data with qualifiers (e.g., "<") will be listed with but summarized without the qualifier.

P-values will be presented in summary tables to two decimal places if > 0.01, to three places if < 0.01 but > 0.001, and to four places if < 0.001 but > 0.0001. However, p-values > 0.045 but < 0.055 will also be presented to three decimal places. P-values < 0.0001 will be presented as "< 0.0001."

Statistical tests will be two-sided and tested at the 0.20, 0.10, and 0.05 significance levels in a hierarchical manner.

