12.1 Efficacy Parameters

12.1.1 VAS and NRS-11

Ear pain will be measured by VAS and NRS-11. Scores will be collected for each ear at Baseline and 10, 20, 30, and 60 minutes post dose.

The VAS consists of a 100 mm line anchored by 2 extremes of pain, with the left anchor representing "no pain" and the right anchor representing "worse pain." Study Participants mark the line where their pain is best represented between the 2 anchors. The VAS score is the distance from the left anchor to the Study Participant's mark.

Confidential Page 18 of 33

NRS-11 pain scores range from 0 to 10, with 0 representing "no pain" and 10 representing the "worst pain possible." NRS-11 \geq 5 reflects moderate to severe pain and is an inclusion criterion.

Listings will show observed values and absolute changes from baseline for each ear separately, for the sum over both ears, and for the maximum score across both ears. For both VAS and NRS-11, decreasing change scores from baseline indicate improvement and this will be footnoted in TFLs.

Endpoints

The following endpoints will be calculated for both VAS and NRS-11, unless otherwise indicated, using (a) the sum of scores over both ears, and (b) the maximum score across both ears:

- PID_{t_i} where i = 1 to 4 and t_1 , t_2 , t_3 , $t_4 = 10$, 20, 30, and 60 minutes post dose, respectively, and PID_{t_i} = score at time t_i score at baseline (ie, change from baseline).
- SPID_t I defined as

$$SPID_{t_{-}I} = \sum_{i=1}^{I} PID_{t_{-}i} (t_i - t_{i-1})$$

where I = 1 to 4, t_0 is baseline, and t_1 , t_2 , t_3 , t_4 are time points 10, 20, 30, 60 minutes post dose, respectively. For example, SPID₂ is the sum of changes from baseline at 10 and 20 minutes post baseline weighted by time (in minutes) since the previous measurement.

- Percent change from baseline (per inclusion criteria, baseline VAS and NRS-11 are unlikely to be 0).
- Presence of any pain, defined as score > 0 at 10, 20, 30, and 60 minutes post dose.
- Improvement categorized as "worsening" (positive change score), "no change" (0 change score), "improvement" (negative change score) at 10, 20, 30, and 60 minutes post dose.

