- Time to pain relief defined as time point (10, 20, 30, 60 minutes post dose or no pain relief) at which relief was achieved, where "relief" is defined as score < 5 for NRS-11 and at least a 30 mm decrease from baseline for VAS. In the unlikely event that a Study Participant has a baseline VAS less than 30 mm, they will be excluded from the VAS analysis of time to pain relief.
- Response, defined as a 25%, 50%, and 75% reduction in score, at 10, 20, 30, and 60 minutes post dose.

Summaries and Analyses (see Section 13)

• PID_{t_i} will be analyzed using mixed model for repeated measures (MMRM). A summary table will include least-squares (LS) means and standard errors (SEs) for each treatment group and the estimate of treatment group difference with 80, 90, and 95% confidence intervals (CIs) for the difference and associated p-values. LS means and SEs will also be graphically displayed using a line chart. In addition, 80, 90, and 95% CIs and associated p-values for within-group mean changes from baseline will be included in the summary table.

Confidential Page 19 of 33

- SPID_{t_I} will be analyzed using mixed model for repeated measures (MMRM). A summary table will include least-squares (LS) means and standard errors (SEs) for each treatment group and the estimate of treatment group difference with 80, 90, and 95% confidence intervals (CIs) for the difference and associated p-values. LS means and SEs will also be graphically displayed using a line chart. In addition, 80, 90, and 95% CIs and associated p-values for within-group mean changes from baseline will be included in the summary table.
- Response will be analyzed using general estimating equations (GEE). A summary table will include LS means and SEs for each treatment group and the estimate of treatment group difference with 80, 90, and 95% CIs for the difference and associated p-values. Crude response rates will be graphically displayed using a bar chart.
- Percent change from baseline, presence of pain, improvement category, and time to pain relief will be summarized in tables but will not be subjected to statistical inference.

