13. STATISTICAL METHODS

13.1.1 Methods of Analysis for Repeated Continuous Endpoints

Treatment group comparisons on endpoints that are continuous variables assessed repeatedly will be done using MMRM with change from baseline as the dependent variable; nominal visit (time), treatment group, and treatment-by-time interaction as fixed effects; baseline observation as a fixed-effect covariate (if applicable); and correlated errors within subject. Site will be included as a random effect if doing so appreciably affects treatment effect estimates. Covariance estimation will be done using restricted maximum likelihood. Error degrees of freedom will be calculated using the Kenward-Rogers approximation. Unstructured covariance for the residuals (R matrix) will initially be specified but other covariance structures may be explored by examining the R matrix and using goodness-of-fit measures (e.g., Akaike's Information Criterion). If a structured covariance is used, the sandwich estimator will be used for SEs and error degrees of

Confidential Page 22 of 33

freedom will be calculated using the between-within method. Model-based LS means will be reported for each treatment group, along with CIs and p-values for treatment group comparisons, for each nominal visit. A p-value for treatment group comparison over all visits will only be reported if there does not appear to be a treatment-by-time interaction, either based on the interaction p-value or by a descriptive examination of the data, and the term for treatment-by-time interaction will not be included in the model.

Model assumptions will be evaluated using diagnostic tools such as Q-Q and scatter plots of residuals, and sensitivity analyses using alternative methods (e.g., rank-based, GLM at individual time points) will be considered if there appear to be substantial deviations from model assumptions. Outlier assessment will be done using visual inspection (e.g., box-and-whisker plots) and potential outliers will be investigated for data entry accuracy and biological consistency. If unexplainable outliers are present, a sensitivity analysis may be done excluding the outliers to assess their effect on the analysis conclusion.

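### If the repeated-measures model moves to a structured covariance, SAP 13.1.1 requires a sandwich SE and names no small-sample correction; with about 24 participants, a classical sandwich would make the intervals on that optional branch modestly too narrow

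*SAP*

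**What the plan says.** SAP 13.1.1 sets out the MMRM for repeated continuous endpoints: visit, treatment and their interaction as fixed effects, a baseline covariate, REML, an unstructured residual covariance to begin with, and Kenward-Roger df. Other structures may then be explored by looking at the R matrix and at fit measures such as AIC. For that case the SAP states: "If a structured covariance is used, the sandwich estimator will be used for SEs", and error degrees of "freedom will be calculated using the between-within method". It does not say whether the sandwich is small-sample corrected, or which part of the between-within df applies to the per-visit treatment contrasts.

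SAP 12.1 applies this model to PID, SPID and PGIC. For PID and SPID the tables give "the estimate of treatment group difference with 80, 90, and 95% confidence intervals (CIs) for the difference and associated p-values"; PGIC is reported likewise. On testing, SAP 8.3 says: "Statistical tests will be two-sided and tested at the 0.20, 0.10, and 0.05 significance levels in a hierarchical manner". SAP 13.1.5 makes no multiplicity adjustment. On size, SAP 5 says "Approximately 24 Study Participants will be randomized", and Protocol 5.2.1 has them "randomly assigned in a ratio of 1:1 (12 subjects per arm").

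For PGIC, Protocol 5.2.6.1 specified an unstructured covariance only. SAP section 15 lists other changes to that model but not the option of a different structure. The protocol lets the SAP take precedence, so this is an unlisted change and not a conflict.

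**The concern.** The default branch has a small-sample method and the alternative branch, as worded, does not. A classical sandwich variance is built from residuals that are too small on average, because fitting the mean uses up degrees of freedom. With hundreds of clusters this is negligible; with 24 it is not. If the between-within rule also gives the per-visit contrasts the large within-subject df, the t quantile shrinks as well.

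Calibrated intervals at three confidence levels are the main inferential output for efficacy here. The move to the alternative branch has no convergence trigger, ordered list or binding criterion. A change of covariance structure could therefore narrow the intervals for reasons unrelated to the data's precision, and could carry a borderline result across one of the three thresholds.

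**Working it through.** **No plan figure to reproduce.** Protocol 5.2.1 and SAP 5 give a sample size without power, effect size or SD, and the SAP states no error rate for the alternative branch. The benchmark is nominal coverage of 80/90/95%.

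**Inputs.** 24 participants, 12 per arm (Protocol 5.2.1); four post-dose times plus baseline (SAP 12.1.1); fixed effects as in SAP 13.1.1. Data are taken as complete, since SAP 13.1.4 expects no more than 10% of participants to have missing values.

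**Degrees of freedom.** Between-subject: 24 − 3 (intercept, treatment, baseline) = 21. Within-subject: 24 × 4 = 96 observations, less 24 subjects, less 6 (3 time and 3 interaction terms) = 66. Which of these the SAP intends is not stated, so both are carried.

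**Analytic check.** In a balanced complete design with 3 between-subject parameters, the uncorrected sandwich variance is about 21/24 of the unbiased one, so the SE is about √(21/24) = 0.935 of its proper size (roughly 6% too small). Coverage is then 2·F(t_q × 0.935) − 1, where F is the t distribution with 21 df and t_q is the quantile actually used.

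| Nominal | t_q, 66 df | Coverage | t_q, 21 df | Coverage |
|---|---|---|---|---|
| 80% | 1.294 | 76.1% | 1.323 | 77.1% |
| 90% | 1.668 | 86.6% | 1.721 | 87.8% |
| 95% | 1.997 | 92.4% | 2.080 | 93.5% |

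The df choice alone changes width by 1.294/1.323 = 0.98 at 80% and 1.997/2.080 = 0.96 at 95%, that is 2 to 4%. The rest is the SE.

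**Simulation.** Normal data, no treatment effect, baseline covariate, compound-symmetric truth, compound symmetry fitted on the structured branch, 10,000 runs (Monte Carlo SE about 0.4 points at 80%). Coverage of the 60-minute treatment difference:

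| Method | 80% | 90% | 95% |
|---|---|---|---|
| Unstructured, Kenward-Roger (default) | 79.9 | 89.8 | 94.8 |
| Uncorrected sandwich, 66 df | 76.1 | 86.7 | 92.2 |
| Uncorrected sandwich, 21 df | 77.2 | 87.8 | 93.2 |
| Kauermann-Carroll type sandwich, 21 df | 79.7 | 89.7 | 94.8 |
| Mancl-DeRouen type sandwich, 21 df | 82.5 | 91.7 | 96.1 |

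With 66 df the two-sided error is 100 − 76.1 = 23.9%, 100 − 86.7 = 13.3% and 100 − 92.2 = 7.8%, against 20, 10 and 5%. The uncorrected intervals are 8 to 10% narrower than the default with 66 df, and about 6% narrower with 21 df.

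**When the structure is wrong.** The truth is now heteroscedastic and autoregressive in type, with compound symmetry fitted (2,500 runs), again at 60 minutes:

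| Method | 80% | 90% | 95% |
|---|---|---|---|
| Uncorrected sandwich, 66 df | 74.6 | 85.7 | 92.1 |
| Model-based Kenward-Roger | 66.6 | 78.8 | 86.8 |
| Kauermann-Carroll type, 21 df | 78.3 | 88.8 | 94.9 |
| Mancl-DeRouen type, 21 df | 80.9 | 90.8 | 96.2 |

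The default covered 78.5/88.9/94.8% in these runs. At 10 minutes under the same truth, the uncorrected sandwich with 66 df lost less (78.2/88.0/92.9%), while model-based Kenward-Roger was far too wide (93.3/97.6/99.3%). The model-based failure therefore goes in either direction depending on the visit.

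**The case against.** The strongest defence has four parts.

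First, pairing a sandwich SE with an imposed structure is a coherent choice, because it protects against choosing the wrong structure. This stands. The second simulation shows the uncorrected sandwich doing clearly better at 60 minutes than model-based Kenward-Roger under a wrong structure, so the sandwich should be corrected and not removed.

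Second, the SAP does not say that the sandwich is uncorrected or that 66 df will be used. This also stands. A reader might infer that the plan mandates both, but both are readings of silence. The under-coverage with a classical sandwich does not depend on the df reading; it does depend on the sandwich being the classical one.

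Third, the branch is optional and the endpoints are exploratory. A reader might infer that the trial's efficacy intervals are too narrow in general. The documents do not support that: the unstructured Kenward-Roger model is fitted first and is well calibrated, few missing data are expected, and nothing shows that another structure will be needed. Nor do they support the inference that structures may be picked for significance, since SAP 13.1.1 points to the R matrix and goodness of fit. What remains is that the choice is made on the data without a binding rule.

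Fourth, the effect is modest, and the protocol's threshold is already p < 0.20. That is true and limits the weight of the point. It is not a reason to report an interval as 95% when it covers about 92 to 93%.

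**Conclusion.** The concern holds for the alternative branch only, and on the condition that the unqualified term means the classical sandwich. In that case coverage of the 60-minute treatment difference falls short by about 3 to 4 points at 80% and 2 to 3 points at 95%, mostly through an SE about 6% too small. The primary safety objective and the default efficacy analysis are untouched.

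The figures assume 24 complete participants, normal data, no site effect and the covariance structures described above, since the documents give no SD or correlation. They come from the common model and sample size; SPID and PGIC, the latter a seven-point scale, were not simulated separately. This should be put right before database lock, but it does not threaten the trial's main conclusion.

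**What to change.** Amend SAP 13.1.1 to say:

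1. The unstructured model with Kenward-Roger is the reported analysis whenever it converges.
2. Only on non-convergence, structures are tried in a fixed, listed order (for example heterogeneous Toeplitz, then AR(1), then compound symmetry), and the first to converge is used.
3. On that branch, SEs come from a named bias-corrected sandwich (for example Kauermann-Carroll or Mancl-DeRouen), with between-subject df of about 21 for the treatment contrasts.

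Do not substitute model-based Kenward-Roger on a structured covariance. List the covariance option for PGIC in SAP section 15.

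The cost is a few sentences and a software setting. Intervals on this branch become slightly wider than under the present wording. The Kauermann-Carroll type roughly restores the default's width. The Mancl-DeRouen type is mildly conservative, covering about 82 to 83% at nominal 80% when the fitted structure is right.

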5.2.6 Efficacy Analyses

5.2.6.1 Exploratory Analysis

Pain Intensity Difference (PID) & Sum Pain Intensity Difference (SPID) will be calculated as follows:

• PID will be calculated as:

$$PID_t = PI_t - PI_{Baseline}$$

Where t is the post-dose assessment timepoint

Where baseline is the predose assessment timepoint

• SPID will be calculated as:

$$SPID_{ti-ti+n} = \sum_{ti}^{ti+n} (PID_i) * (t_{i+1} - t_i)$$

Where PID_i is the pain intensity difference score calculated at each post-dose timepoint

Where t_i is the scheduled assessment time

Analyses for Continuous Data

PID (change from Baseline) will be computed for each post-dose assessment timepoint (10, 20, 30, and 60 min). Data will be analysed using a longitudinal mixed model for repeated measures with fixed effects for treatment, time, treatment-by-time interaction, study site, and baseline pain score. Subject will be the random effect. Treatment differences from control (placebo) will be estimated from the Least Squares Means (LSM) from the analysis model along with 80% confidence intervals (CIs) and associated 2-sided p-values. If significance is found using 80% CIs, 90% and 95% CIs will also be tested. Only observed cases will be included in the PID computations. Graphical displays of the LSM change from Baseline will also be provided by treatment.

Descriptive summaries for each PID timepoint will be provided by treatment along with the model output for test differences in the LSM. PID analyses will be conducted for both NRS-11 and VAS pain scales.

SPID will be analysed using a linear model analysis of variance (ANOVA) with fixed effects for treatment, site, and baseline pain score. Treatment differences from control (placebo) are estimated using the LSM from the analysis model along with 80% CIs and associated 2-sided p-values. If significance is found using 80% CIs, 90% and 95% CIs will also be tested. SPID analyses will be conducted for both NRS-11 and VAS pain scales. Missing data will be handled using the Last Observation Carried Forward imputation method.

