4.2.2 Exploratory Endpoints

Exploratory endpoints are related to efficacy and success of blinding:

- Response on ear pain scores at 10, 20, 30, and 60 minutes post dose using the VAS and the NRS-11
- Pain Intensity Difference (PID) from Baseline of the VAS and the NRS-11 at 10, 20, 30, and 60 minutes post dose
- Sum Pain Intensity Difference (SPID) of the VAS and the NRS-11 over 60 minutes post dose
- Time to ear pain relief in affected ear(s), recorded as change from moderate/severe pain to mild or no pain using the VAS and the NRS-11
- PGIC measured at 10, 20, 30, and 60 minutes post dose
- CGI-I scale measured at 60 minutes post dose
- Presence of AOM symptoms
- Response on the Blinding Index at 60 minutes post dose
- Response on Device Experience Questionnaire Subject
- Response on Device Experience Questionnaire Study Staff Administering Treatment

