13.1.3 Method of Analysis for Repeated Binary Endpoints

Treatment group comparisons on binary endpoints assessed repeatedly will be done using GEE with nominal visit (time) and treatment group as main effects, treatment-by-time as an interaction term, an appropriate baseline value as a covariate (if applicable); and correlated errors within subject.

Confidential Page 23 of 33

The working correlation structure will initially be specified as unstructured but other structures may be explored by examining the covariance matrix and using goodness-of-fit measures (e.g., Quasilikelihood under the Independence model Criterion). P-values for treatment group comparisons will be reported for each nominal visit. A p-value for treatment group comparison over all visits will only be reported if there does not appear to be a treatment-by-time interaction, either based on the interaction p-value or by a descriptive examination of the data, and the term for treatment-by-time interaction will not be included in the model.

Alternative approaches for the analysis of binary endpoints, such as random-effects models (including site as a random effect if doing so appreciably affects treatment effect estimates), chi squares tests of association or Fisher's exact tests, may be considered.

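### For cumulative SPID, the rule that reports an all-visit p-value only when no treatment-by-time interaction appears is itself a test of drug effect, and the common-effect model it leads to is misspecified

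*SAP*

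**What the plan says.** SAP 13.1.1 governs every repeatedly measured continuous endpoint. The MMRM has time, treatment and their interaction as fixed effects, with an unstructured covariance to begin with. LS means, confidence intervals and p-values are given at each nominal visit. A further test is conditional: "A p-value for treatment group comparison over all visits will only be reported if there does not appear to be a treatment-by-time interaction". When that test is reported, "the term for treatment-by-time interaction will not be included in the model". SAP 13.1.3 repeats the rule for binary endpoints under GEE, and both sections let the decision be made "either based on the interaction p-value or by a descriptive examination of the data". Neither section gives a cut-off for the interaction p-value.

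SAP 12.1.1 defines SPID at 10, 20, 30 and 60 min as a running total. Its example, the 20-min value, "is the sum of changes from baseline at 10 and 20 minutes post baseline weighted by time (in minutes) since the previous measurement". The four values are analysed by MMRM, so 13.1.1 applies, and no exception is made for SPID. The protocol had planned a model without a time factor (5.2.6.1): "SPID will be analysed using a linear model analysis of variance (ANOVA) with fixed effects for treatment, site, and baseline pain score". SAP section 15 records the change. The endpoint listed in SAP 4.2.2 is "Sum Pain Intensity Difference (SPID) of the VAS and the NRS-11 over 60 minutes post dose".

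**The concern.** For an endpoint measured afresh at each visit, declining to pool when the effect varies with time is a common convention. A cumulative endpoint is different. If the drug lowers pain by the same amount at every visit, the SPID difference grows with time, so an interaction exists by construction. Whether the all-visit SPID p-value appears then depends on the effect it is meant to measure. If it does appear, it comes from a model that assumes the SPID difference is equal at all four times, which holds only when there is no effect after 10 min.

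For PID, PGIC and response the issue is narrower. Whether an overall p-value exists is settled after the results are seen, by one of two routes, neither with a stated criterion.

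**Working it through.** The documents give no effect size, SD, correlation or power, so there is no planned figure to reproduce.

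**Inputs from the documents.** Weights t(i) - t(i-1) = 10, 10, 10, 30 min (SAP 12.1.1); 12 per arm (Protocol 5.2.1); unstructured covariance initially (SAP 13.1.1); two-sided testing at 0.20, 0.10 and 0.05 (SAP 8.3).

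**Assumptions.** NRS-11 PID SD 2.5; correlation between visits 0.5 or 0.8 exchangeable, or 0.8 AR(1); constant PID effect of 0, 1, 2 or 3 points; complete data; interaction cut-off 0.05, 0.10 or 0.20.

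**Step 1: what the gate tests.** From the SAP formula, SPID(I) - SPID(I-1) = PID(I) × [t(I) - t(I-1)]. The successive increments are therefore 10×PID20, 10×PID30 and 30×PID60. No treatment-by-time interaction in SPID means no treatment difference in any of these increments, that is, no effect on PID at 20, 30 and 60 min. Only an effect confined to 10 min leaves no interaction.

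**Step 2: a constant effect.** With the same PID difference d (negative is benefit) at every visit, the SPID differences are 10d, 20d, 30d and 60d. Their average is (10 + 20 + 30 + 60)d/4 = 30d, which is -60 for d = -2.

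**Step 3: how often the all-visit test is withheld.** Simulated with 4000 trials per setting, baseline as covariate and a Wilks test on the SPID increments. Ranges are over the three correlation structures.

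| Constant PID effect | Cut-off 0.05 | Cut-off 0.10 | Cut-off 0.20 |
|---|---|---|---|
| None | 4-5% | 10% | 20% |
| 1 point | 10-13% | 19-23% | 31-36% |
| 2 points | 31-41% | 44-54% | 61-71% |
| 3 points | 64-77% | 76-87% | 87-94% |

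With the same constant effects, the interaction test on PID stays at about 5%, 10% and 20%. The effect-dependence is specific to SPID.

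**Step 4: what is reported when the gate stays open.** With V the covariance of the four SPID values, δ the vector of SPID differences and 1 a vector of ones, the common-effect estimate is (1'V⁻¹δ)/(1'V⁻¹1). Substituting the running-sum structure and a constant d:

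- exchangeable ρ: 10d(1 - ρ)/(1 + 2ρ). For ρ = 0.5 this is 10d × 0.5/2 = 2.5d; for ρ = 0.8 it is 10d × 0.2/2.6 = 0.77d;
- AR(1) ρ: 10d(1 - ρ). For ρ = 0.8 this is 2d.

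For d = -2 these give -5.0, -1.5 and -4.0, against the true average of -60. The simulated means were -1.5 to -4.8, and p < 0.20 occurred in only 22-25% of trials. The SAP allows other covariance structures. One that weighted the four SPIDs equally would return 30d, so the size of this error belongs to the unstructured starting choice.

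**Step 5: what remains available.** The 60-min SPID comparison has no gate. Under the same assumptions it reaches p < 0.20 in 41-45% of trials for 1 point, 77-85% for 2 points and 96-98% for 3 points.

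**The case against.** The strongest reply is that little is lost. SAP 13.1.1 requires per-visit comparisons whatever the interaction shows, SAP 12.1.1 requires the SPID treatment difference with its intervals and p-values, and SAP 13.1.3 requires per-visit p-values for response. The 60-min SPID result, which is the listed endpoint, is therefore always reported. A reader might infer that the rule conceals an effective drug or amounts to selective reporting. The documents do not support that, because what the gate controls is one additional p-value. As that p-value comes from a misspecified model, withholding it when the SPID differences fan out can even be called protective.

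Three further points stand. The withholding rates depend strongly on an assumed cut-off and effect size. Not pooling when an interaction is present is ordinary practice for PID and response. Efficacy is exploratory, with multiplicity openly unadjusted (SAP 13.1.5).

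The objection does not rescue the rule for SPID. The plan still calls for a test whose appearance depends on the drug effect and whose estimate, when it appears, does not describe that effect. Nor does it supply the missing criterion for the other endpoints.

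**Conclusion.** The point holds, at minor to moderate severity. That the SPID gate tests for a PID effect after 10 min is algebra on the SAP's own formula and needs no assumption. The sizes do need assumptions: for a constant 2-point effect with SD 2.5 and 12 per arm, withholding in about 31-71% of trials depending on cut-off and correlation, and a common-effect estimate of about -1.5 to -5 against -60. SD, correlation, effect and cut-off are not in the documents, and withholding is a probability, not a certainty. The main SPID result is untouched, because the 60-min comparison is always reported. For PID, PGIC and response the finding is only that a data-dependent reporting decision has no stated criterion.

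**What to change.** In SAP 12.1.1 and 13.1.1, compute no over-visits test for cumulative SPID, and name SPID at 60 min as its single between-group comparison. This matches the endpoint in SAP 4.2.2.

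In 13.1.1 and 13.1.3, delete the conditional rule. For PID, PGIC and response, keep the interaction term and always report one pre-specified contrast, for example the average of the four time-specific differences, alongside the per-visit results.

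The cost is SAP wording and one contrast statement per model. No new data or change in conduct is needed.
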